influences chronic pain is limited, but data from adult survivors reflect similar trends as observed in the general population with risk factors including female sex, lower educational attainment, unemployment, household income <\$20,000, and Black and Hispanic race/ethnicity.^{18, 23} Importantly, childhood cancer and its treatment can have a substantial negative impact on *parental* socioeconomic situation. A recent systematic review revealed a high level of disruption in parental employment, income loss, and increased perceived financial burden following a child's cancer diagnosis.²⁴ In addition, >30% of families reported experiencing household material hardship at least 1 year-off therapy.²⁵ These potential threats to parental socioeconomic position likely influence the experience of chronic pain and its management for adolescent survivors of childhood cancer.

Intermediary determinants of health: In addition to variables that shape *socioeconomic position*, intermediary determinants (middle part of Figure 1) including *behavioral* and *psychosocial factors*, *material conditions*, and *healthcare systems* may also be associated with chronic pain in childhood cancer survivors. In terms of *behavioral factors*, sedentary behavior and low cardiorespiratory fitness have been associated with increased risk of pain among children.²⁶ A recent study revealed that drinking to intoxication was associated with a 3-fold increased likelihood of persistent pain among survivors of childhood cancer.²⁷ Related to *psychosocial factors*, adolescents with chronic pain often experience mental health comorbidities²⁸, including anxiety²⁹ and depression.³⁰ Fatigue and sleep disturbance are common among adolescents with chronic pain.³¹ Sleep is a potential mechanism underlying the transition from acute to chronic pain in youth,³² and fatigue has been shown to mediate the relationship between pain intensity and pain-related disability in youth with chronic pain.³³ Parental affective factors, including anxiety have been associated with increased child pain intensity and analgesic use.³⁴ As adolescent development is characterized by greater autonomy from parents and increased emphasis on peer relations, it is not surprising that peer relationship quality moderates associations between parent and adolescent cognitive and behavioral pain responses.³⁵

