3.3 Inclusion Criteria for feasibility study

- 3.3.1 Hispanic, non-Hispanic Black, and non-Hispanic White 10–17-year-old survivors of pediatric cancer
- 3.3.2 At least one-year post treatment completion
- 3.3.3. Pain present over the past 3 months and pain at least once per week
- 3.3.4. Pain interfering with at least one area of daily functioning

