Adverse event monitoring: Patient reports of AEs will be surveyed weekly, with symptoms reported for the prior tDCS sessions. Information will be collected by incident participant reporting and direct questioning using the patient report of incidence of side effects (PRISE).⁸⁵ Side effects will be assessed during weekly sessions. The PRISE assesses the presence of side effects for several biological systems. For each system (skin, nervous, eyes/ears, sleep, other), participants indicate the presence of a side effect, and if present, the tolerability of the side effect (tolerable or distressing). The PRISE includes commonly reported side effects of tDCS: tingling, itching sensation, burning sensation, pain, headache, fatigue, difficulty concentrating, and nervousness.⁸⁶ Participants will also be asked to report any other symptoms experienced during the tDCS session.

Figure 4a. Study Schema – Virtual Focus Groups

[figure not shown]
[figure not shown]

Figure 4b. Study Schema – Feasibility Pilot Study

4.2 Study Procedures:

All cultural adaptation processes will occur separately, but in parallel, for non-Hispanic Black and Hispanic participants. See detailed descriptions of procedures in 4.1 Design and Study Overview above.

Expert Panel via virtual meetings - 2 to 4 (1) hour virtual meetings with non-Hispanic Black and Hispanic parents and young adult survivors of childhood cancer and key study investigators. Sessions will be audio-recorded and transcribed verbatim.

Stakeholder Focus Group via virtual focus groups - (2-4) 45-minute sessions with non-Hispanic Black and Hispanic adolescent survivors of childhood cancer. Sessions will be audio-recorded and transcribed verbatim.

Preliminary Content Adaptations – based on results of qualitative analysis of stakeholder feedback.

Iterative Adaptation Process via virtual focus groups - (2-4) 45-minute sessions where adaptations will be presented to lived experience stakeholders (non-Hispanic Black and Hispanic survivors of childhood cancer with chronic pain). Sessions will be audio-recorded and transcribed verbatim.

Feedback meetings via virtual focus groups – (2-3) with 5-7 non-Hispanic Black and 5-7 Hispanic adolescent survivors who participated in previous sessions to review final program adaptations. Sessions will be audio-recorded and transcribed verbatim.

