7.0 SAFETY AND ADVERSE EVENT REPORTING REQUIREMENTS

7.1 Adverse Events (AEs)

Adverse events will be monitored from the start of the study. Participants will be instructed to report all AEs during the study and will be assessed for the occurrence of AEs throughout the study. Weekly PRISE forms will be completed.

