7.2 Definitions

Adverse Event (AE): Any untoward medical occurrence associated in a study participant after the beginning of the study. Adverse Events will be graded by the NCI CTC AE version 5.0. Participants will be instructed to report all AEs during the study and will be assessed for the occurrence of AEs throughout the study.

Serious Adverse Event (SAE): Any adverse event temporally associated with the subject's participation in research that meets any of the following criteria:

- results in death;
- is life-threatening (places the subject at immediate risk of death from the event as it occurred);
- requires inpatient hospitalization or prolongation of existing hospitalization;
- results in a persistent or significant disability/incapacity;
- results in a congenital anomaly/birth defect; or
- any other adverse event that, based upon appropriate medical judgment, may jeopardize the subject's health and may require medical or surgical

intervention to prevent one of the other outcomes listed in this definition.

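### The side-effect form (PRISE) has no pre-stimulation administration, so symptoms already present can be reported as tDCS side effects and cannot be told from new ones

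*Combined protocol and SAP*

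**What the plan says.** Section 4.1 (adverse event monitoring) gives the schedule: "Patient reports of AEs will be surveyed weekly, with symptoms reported for the prior tDCS sessions". Section 7.1 repeats it: "Weekly PRISE forms will be completed". Section 7.3 again describes a weekly survey and adds that the version used is a modified PRISE.

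The content is set out in 4.1: "The PRISE includes commonly reported side effects of tDCS: tingling, itching sensation, burning sensation, pain, headache, fatigue, difficulty concentrating, and nervousness". For each body system, "participants indicate the presence of a side effect, and if present, the tolerability of the side effect (tolerable or distressing".

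Entry under 3.3 requires "Pain present over the past 3 months and pain at least once per week". Section 2.1 says of such patients: "Fatigue and sleep disturbance are common among adolescents with chronic pain". Section 7.2 defines an adverse event as "Any untoward medical occurrence associated in a study participant after the beginning of the study" and gives no rule for symptoms that were there before.

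The first stimulation is a single tDCS session given during training (4.1). Twelve sessions are planned, two a week for six weeks. Table 2 lists the baseline and post-intervention questionnaires, and the PRISE is not among them. The activity table in 5.1 has no PRISE row. Section 9.0 plans no adverse event analysis.

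**The concern.** Several PRISE items describe complaints that adolescents with chronic pain may have whether or not they are stimulated. A form that records presence, given only after stimulation has begun, cannot show onset. If a participant ticks headache in week 2, the data do not reveal whether it began with tDCS or has been there for a year.

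What is at stake is the side-effect profile that the pilot hands to the R33 trial. Background symptoms can raise the counts in both arms and make a true device effect harder to see. A missing baseline answer cannot be recovered once the training session has taken place.

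**Working it through.** The documents state no side-effect rate or threshold, so there is no figure to reproduce. The check is of the schedule and the form, followed by illustrations whose rates are all assumed.

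**1. Is there a pre-stimulation form?** Sections 4.1, 7.1 and 7.3 each say weekly. Section 4.3 with Table 2, the 5.1 table and the rest of section 7 name no PRISE before training. Section 7.1 says that events are monitored from the start of the study, but that is a general statement and not a form.

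**2. Can the form separate old from new?** As described, each answer has two parts, presence and tolerability. No field for onset, for change from before or for relatedness is described. Section 7.3 has the investigator judge seriousness, with no causality step for ordinary events.

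**3. What do the baseline questionnaires cover?**

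| PRISE content | Baseline counterpart in 4.3 / Table 2 |
|---|---|
| Pain | BPI severity items and body diagram |
| Fatigue | PROMIS Fatigue (past 7 days) |
| Nervousness | PROMIS Anxiety (past 7 days), GAD-2 |
| Sleep | ASWS, PROMIS Sleep-Related Impairment |
| Headache | None described; the body diagram locates only where pain is worst |
| Difficulty concentrating | None described |
| Tingling, itching, burning | None described |

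The counterparts use other formats and recall windows, and no section says they will be used to read PRISE answers.

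**4. How large could the background be?** Assume no device effect throughout, and independence between weeks.

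- Pain on d random days a week, two session days a week, any session-day pain ticked. The chance that a week overlaps is p = 1 − C(7−d, 2)/C(7, 2), and the chance of at least one report in six forms is 1 − (1 − p)^6. For d = 1, the entry minimum, p = 1 − 15/21 = 0.286, and 1 − (5/7)^6 = 0.867, or about 26 of 30. For d = 2, p = 1 − 10/21 = 0.524 and the result is 0.988, or about 29.7 of 30.
- If participants hold strictly to the session window, the per-form background q is lower. With 1 − (1 − q)^6:

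| q per form | At least one report | Of 30 |
|---|---|---|
| 5% | 26.5% | 7.9 |
| 10% | 46.9% | 14.1 |
| 20% | 73.8% | 22.1 |
| 30% | 88.2% | 26.5 |

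If the same participants tend to report each week, these proportions fall.

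**5. Does the sham arm settle it?** Arms are 15 and 15 (5 + 5 in each of three groups). Assume tDCS causes the symptom in 30% of those otherwise free of it, so the active rate is b + (1 − b) × 0.30 for background b. Fisher's exact test, two-sided 0.05:

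| b (sham) | Active | Power |
|---|---|---|
| 0 | 0.30 | 0.485 |
| 0.10 | 0.37 | 0.267 |
| 0.30 | 0.51 | 0.106 |
| 0.50 | 0.65 | 0.057 |

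**6. Would a baseline form restore power?** No. Take b = 0.60 and a device effect of 0.20 in the rest. Sham is 0.60 and active 0.60 + 0.40 × 0.20 = 0.68, so 15 × 0.08 = 1.2 extra participants. Among those free at baseline there are 0.40 × 15 = 6 per arm, and 0.20 × 6 = 1.2, the same participants. A split of 1/6 against 0/6 gives Fisher p = 1. The gain is in reading each report, not in a test.

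**The case against.** The strongest reply is that the PRISE question is not about symptoms in general. It asks about side effects and ties them to the preceding tDCS sessions. A reader might infer that existing symptoms will be recorded as side effects as a matter of course. The text does not support that: they can be, if the adolescent misattributes them or ignores the window. This stands, and it limits the claim.

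Five further replies deserve weight.

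- The modified form is not shown and might have an onset or attribution field. That also stands; the point rests on the description in 4.1. The schema figures are not shown either.
- Pain and fatigue, the most obvious items, do have baseline measures. This stands in part, since the plan never connects them to the PRISE. The clearer gap is headache, concentration and skin symptoms.
- The sham arm shows background under the same form. It does so on average, but step 5 shows how little 15 per arm can resolve. It also cannot classify an individual report, and 4.1 treats blinding as unnecessary at this stage, so attribution may differ by arm.
- The adverse event definition covers only what occurs after the study begins, which excludes long-standing symptoms on paper. Without a prior answer for the same items, nobody can apply that exclusion reliably.
- No decision depends on the PRISE. Section 9.0 judges feasibility on participation, adherence and acceptability, and the R33 milestones do not mention side effects. This stands in full.

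**Conclusion.** The gap is real and modest. As written, the plan yields weekly side-effect reports with no pre-stimulation answer on the same items, in a sample selected for ongoing pain. Existing and new symptoms cannot be separated from the form as described, least of all for headache, difficulty concentrating and skin symptoms.

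The size is unknown. Two stronger conclusions might be inferred, and neither is supported. One is that the side-effect rates will mostly reflect the underlying condition: the documents give no background rate for any item, and for tingling, itching and burning they offer no reason to expect a high one. The other is that the feasibility result is compromised: it does not use these data. The percentages in the working show what follows from assumed rates and are not predictions.

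Whether effects of the last session are captured is a secondary question. The timing of the final weekly form relative to session 12 is not specified, although participants can also report events themselves.

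**What to change.** - Add a PRISE to the baseline assessment, completed before the training session. Word it as current symptoms, since there are no prior sessions to ask about.
- Add one at the post-intervention assessment, after the last stimulation.
- Give the PRISE a row in the 5.1 table showing baseline, weekly and final forms.
- State in 7.1 or 9.0 that symptoms absent at baseline, or moving from tolerable to distressing, will be reported by arm as new or worsened, beside the raw weekly counts. Keep the sham column in view: symptoms fluctuate, so some will appear as new without any device effect.
- If the modified form already has an onset or attribution field, say so.

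The cost is two short forms per participant (60 over 30 participants) at contacts already planned, with a small added burden, plus a table row and a sentence or two. Raw counts are kept, so no safety information is lost.

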4.3 Study Measures/Observations

Participants in both the focus group and feasibility study will be asked to fill out screening questions as described in the paragraph below.

Demographics: Participants will complete a consent to contact form and, if willing, will complete demographics questions during the screening process to obtain ethnicity, race, and other information needed to target recruitment to meet enrollment goals. If we are unable to confirm diagnosis or other screening information needed to confirm eligibility, study staff will ask the parent/guardian to sign a medical release form to obtain pertinent medical records.

Participants in the feasibility study will complete the outcomes measures listed below (e.g. pain intensity, functional disability) and parents will complete measures of SES, anxiety, depression, and their child's perception of pain and medication use at baseline and post-intervention (Table 2)

Pain intensity and pain interference: The *Brief Pain Inventory-Short Form* (BPI) includes a 4-item pain severity scale.⁸⁷ Participants rate their worst and least pain in the last week, average pain, and current pain.⁸⁸ The BPI pain intensity has good internal consistency in survivors of childhood cancer ($\alpha=0.87$).⁸⁹ This measure includes a body diagram to allow participants to indicate where they experience the most pain. This will be used to inform placement of the anodal tDCS electrode (i.e., right vs. left DLPFC).^{90, 91}

Pain catastrophizing: The *Pain Catastrophizing Scale, Child version* (PCS-C)⁹² is a 13-item self-report measure of overly negative attitudes of pain and it consists of three scales of rumination, magnification, and helplessness. Higher scores indicate more pain catastrophizing.⁹³ This measure has good reliability (Cronbach's $\alpha=0.90$) in a clinical sample of children and adolescents with chronic or recurrent pain.⁹² The *Pain Catastrophizing Scale, Parent version* (PCS-P) is a

modified version of the PCS-C based on parent report of their own catastrophizing related to their child's pain. It assesses the same three factors of rumination, magnification, and helplessness.^{94, 95}

Depression: The *PROMIS Pediatric Depressive Symptoms*⁹⁶ is an 8-item measure of self-reported symptoms of low mood in children and adolescents over the past 7 days. Higher scores indicate greater symptoms. The *Patient Health Questionnaire-2* (PHQ-2) inquires about the frequency of depressed mood and anhedonia over the past 2 weeks. A score of 3 points is the preferred cut-off for identifying possible depression (if the score is 3 or greater, major depressive disorder is likely).⁹⁷

Anxiety: The *PROMIS Pediatric Anxiety*⁹⁶ is an 8-item measure of self-reported symptoms of anxiety symptoms in children and adolescents over the past 7 days. Higher scores indicate greater symptoms. The *Generalized Anxiety Disorder 2-item* (GAD-2) is a very brief and easy to perform initial screening tool for generalized anxiety disorder. A score of 3 points is the preferred cut-off for identifying possible cases and in which further diagnostic evaluation for generalized anxiety disorder is warranted. Using a cut-off of 3 the GAD-2 has a sensitivity of 86% and specificity of 83% for diagnosis of generalized anxiety disorder.⁹⁸

Cancer-related worry: The *Fear of Cancer Recurrence Inventory*⁹⁹ is a 9-item measure developed specifically for survivors of childhood cancer (8-18 years) to assess the presence of fear of recurrence and perceived risk recurrence. Higher scores indicate greater cancer-related worry. Internal consistency is good (ICC=0.88).

Physical functioning: The *PROMIS Pediatric Mobility*¹⁰⁰ is an 8-item measure of self-reported ability at physical activities in children and adolescents in the past 7 days with higher score indicating greater ability. It has excellent test-retest reliability (ICC=0.73) and adequate internal consistency (Cronbach's α =0.73-0.74).¹⁰¹ The *PROMIS Pediatric Upper Extremity*¹⁰⁰ is an 8-item measure of self-upper extremity function in the past 7 days with higher score indicating greater ability. It has excellent test-retest reliability (ICC=0.71) and adequate internal consistency (Cronbach's α =0.62-0.63).¹⁰¹ Both measures are sensitive to change in youth with chronic pain.¹⁰² The PedsQL™ 4.0 Generic Core Scale is reliable and valid in children and adults with cancer and includes a physical functioning scale, an emotional functioning scale, a social functioning scale, a school functioning scale, a total summary score, and both physical and psychosocial health summary scores. The instrument is available in young child, child,

adolescent, and adult versions (scales) if child/adolescent agrees and is able. All versions of this instrument are scored on a 0-100 scale.^{103, 104}

Peer relations: The *PROMIS Pediatric Peer Relationship*¹⁷ is an 8-item measure that assesses the quality of peer relationships. Higher score indicating higher quality. It has excellent test-retest reliability (ICC=0.81) and excellent internal consistency (Cronbach's $\alpha=0.83-0.84$).¹⁰¹

Fatigue: The *PROMIS Pediatric Fatigue*¹⁰⁰ is a 10-item measure that assesses symptoms of fatigue in the past 7 days. Higher scores indicate more fatigue. It has excellent test-retest reliability (ICC=0.76) and internal consistency (Cronbach's $\alpha=0.87$).¹⁰¹

Sleep: The *Adolescent Sleep Wake Scale* (ASWS) short form¹⁰⁵ is a 14-item measure of behavioral sleep patterns in adolescents. Internal consistency was good ($\alpha=0.74-0.84$) in a pooled clinical sample of adolescents with mixed health conditions).¹⁰⁵ Acceptable reliability was reported in a sample of ethnically diverse adolescents from an economically disadvantaged community ($\alpha=0.70-0.90$).¹⁰⁶ We also will use the *PROMIS Sleep-Related Impairment*¹⁰⁷ 8-item measure to allow for assessment of sleep quality during the night as well as the impact of sleepiness on daytime function. This measure is validated for children and adolescents and assess sleep-related impairment over the past 7 days.

Global acceptability and satisfaction with treatment: Acceptability and satisfaction with treatment will be assessed using a 5-point numerical rating scale (NRS) (strongly disagree to strongly agree). The NRS has been recommended for use in pediatric pain clinical trials.¹⁰⁸ Two adapted questions from the modified treatment evaluation inventory will be utilized.^{108, 109} We will also assess patient global impression of change using a single question to assess perceived improvement in pain.^{110, 111}

Opioid Use: At each timepoint participants and/or their parents will be asked to list the names of their medications, doses taken, and the frequency with which the medications were taken over the past 2 weeks.¹¹² Medications will be classified as anti-inflammatory (e.g., nonsteroidal anti-inflammatory drugs); regular (daily) opioids, opioid medication as required (PRN), adjuvant pain medications (e.g., anticonvulsants). Opioid doses will be converted to morphine equivalent doses (MED) using an opioid equivalence table.^{113, 114}

Parent anxiety and depression: Parental affective symptoms will be measured at each time point using the *Patient Health Questionnaire 8-item* (PHQ-8), a

measure of symptoms of major depressive disorder¹¹⁵ and the *Generalized Anxiety Disorder* 7-item (GAD-7), a measure of symptoms of generalized anxiety.¹¹⁶

Table 2.

Outcome Measure	Questionnaire
Pain	Brief Pain Inventory-Short Form (BPI)
	Pain Catastrophizing Scale, Child version (PSC-C)
	Pain Catastrophizing Scale, Parent version (PSC-P)
Depression	PROMIS Pediatric Depressive Symptoms
	Patient Health questionnaire-2 (PHQ-2)
Anxiety	PROMIS Pediatric Anxiety
	Generalized Anxiety Disorder-2 (GAD-2)
Cancer-related worry	Fear of Cancer Recurrence Inventory
Physical functioning	PROMIS Pediatric Mobility
	PROMIS Pediatric Upper Extremity
	PedsQL (ages 8-12 &13-18)
Peer relations	PROMIS Pediatric Peer Relationship
Fatigue	PROMIS Pediatric Fatigue
Sleep	Adolescent Sleep Wake Scale (ASWS) short form
	PROMIS Sleep-Related Impairment
Global acceptability & satisfaction with treatment	2 adapted questions using numerical rating scale
Opioid Use	Medications Survey
	Patient Health questionnaire 8-item (PHQ-8)
Parent anxiety and depression	Generalized Anxiety Disorder 7-item (GAD-7)

4.4 Sites

All collaborating sites (Seattle Children's Hospital, Children's Healthcare of Atlanta, and Texas Children's Hospital) will identify potentially eligible participants, provide the study brochure, and provide the consent to contact form for interested participants. St. Jude will complete the remaining study activities.

